Research Design and Methods: All human subjects' research will be conducted with full approval from the IRB at the University of Texas Health Science at Houston. We will recruit PND patients (N=10) who will be administered a single intravenous infusion of Ketamine either at 0.5 mg/kg or 0.2 mg/kg over 40 minutes in a double-blinded and crossover fashion separated by minimum 7 days, with the order being randomized and balanced across subjects. Two doses will help decide the safe, tolerable and effective dose for PND subjects will undergo a standard screening interview visit to confirm eligibility evaluations including SCID-4 interview (27) and collection of demographic, clinical and medical history. To ensure medical stability, each patient will have a physical examination and urine toxicology screen to rule out the recent undisclosed use of illicit substances. It will also be requested that the patient provide a record of lab results to indicate adequate health for inclusion.

We will pre-screen potential participants over the phone to minimize the invitation to non-eligible participants. Eligible patients that want to participate in the study will be scheduled to have a screening visit to review consent and determine eligibility.

The total duration of the commitment of the study is minimum of 4 weeks. Extension of the timeline can occur depending on the time between the screening visit and the first infusion dose. The total commitment should not exceed 3 months. There will be a minimum 7 days between the 2 infusions. Patients who qualify will complete the infusions on another day at UTHealth Clinical Research Unit at Memorial Hermann-TMC, Houston. University of Texas Health Science Center at Houston Memorial Hermann-TMC [name] or at our Harris County Psychiatric Center (HCPC) where they will be given the ketamine infusion by the study nurse. Patients will be advised to follow the American Association Preoperative Fasting Guidelines prior to infusion.

There will be two appointments where they will be administered a single intravenous infusion of Ketamine either at 0.5 mg/kg or 0.2 mg/kg over 40 minutes in the first infusion visit and a second infusion visit where they will receive the infusion that was not given on the first visit, where there will be a minimum of 7 days between infusions.

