Before the infusion, the psychiatrist and anesthesiologist will evaluate the patient. During the infusion, patients will be asked constantly about "how they feel" and will be monitored continuously by the registered nurse under the supervision of an Anesthesiologist. EKG and pulse-oximetry will be monitored throughout the procedure to

check for hemodynamic changes. After the completion of 40 min infusion, patients will rest for two-four hours under the observation of clinical nurse.. After the infusion both psychiatrist and anesthesiologist will evaluate the patient. Patients may complete clinical questionnaires after this session at HCPC or CRU for approximately 30 minutes. After the first infusion, patients will be contacted one day after over the phone and after the second infusion, patients will be contacted one day after and 7 days after the infusion. During the phone call, patients will be asked about their physical health, will be asked about adverse events and respond questionnaires that evaluate mood status.

Recruitment: The current project will ensure robust and timely recruitment through coordination with ongoing studies at the UT Center of Excellence on Mood Disorder (CEMD) ([name], Departmental Chair). [name] runs a perinatal clinic focused on pregnant or postpartum women with mood disorders in the psychiatry department. [name] also collaborates with [name], UTHealth Department of Obstetrics, Gynecology and Reproductive Sciences on a postpartum research project. Additionally, a large research participant registry has been set up by this UT center (n = 4952 over the last 5 years, of which 80% have a mood disorder history).

Recruitment will also be facilitated through the UT Research Match program. On average, 200 patients have a higher report of depression and mental health problems in the last year and of which nearly 100 patients had higher EPDS scores that meet PND criteria. The perinatal psychiatry clinic will facilitate clinical recruitment. Subject recruitment will include initial identification of cohort pool using selection criteria and subsequent review of identified patient records before final vetting and consent.

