IRB NUMBER: HSC-MS-18-0416
IRB APPROVAL DATE: 06/26/2019

Urine pregnancy test	X	X		X			
Vital Signs	X	X		X			
Height and Weight measurement	X						
Blood Collection		X	X ¹	X	X ²		
Structured Clinical Interview for DSM-IV Axis I Disorders (SCID-I)	X						
Hamilton Depression Rating Scale (HAM-D-17)	X	X	X	X	X	X	X
Montgomery-Asberg Depression Rating Scale (MADRS)	X	X	X	X	X	X	X
Edinburgh Postnatal Depression Scale (EPDS) scale	X	X	X	X	X	X	X
Young Mania Rating Scale (YMRS)	X		X		X		
Clinical global improvement (CGI)	X		X		X		
Brief Psychiatric Rating Scale (BPRS)	X		X		X		
Generalized Anxiety Disorder (GAD-7)	X	X	X	X	X	X	X
Columbia Suicide Severity Rating Scale (C-SSRS)	X		X		X		
Hamilton Anxiety Rating Scale (HAM-A)	X		X		X		
Snaith-Hamilton pleasure scale (SHAPS)	X		X		X		
Beck Depression Inventory (BDI)	X	X	X	X	X	X	X
AE Report	X		X		X	X	X
Concomitant Medications	X		X		X		
Study Contact Card given			X		X		

¹ Done at 30 minutes after infusion (+/-10), 2 hours after infusion (+/- 30 minutes) and 4.5 hours after infusion. IRB NUMBER: HSC-MS-18-0416

Patients that are unable to arrive to the appointment with a caregiver will be reimbursed for 1-2 hours of transportation to and from the infusion days. They will receive a phone call that same day to ensure safe arrival home. UTH Health IRB APPROVAL DATE: 06/26/2019

All of the above clinical questionnaires will be completed at the screening visit as well as on the ketamine infusion day, except the SCID-I, which will only be completed at the screening.

All data collected on paper forms will be stored in locked cabinets, while electronic data is stored on our secure password protected server (maintained by the UTHealth Medical School Information Technology Department). All electronic records will identify study participants only by a study code, and the electronic file linking codes to individual identifiers will be destroyed once data collection is complete.

Patients will arrive fasting from midnight on study visit day have blood draws and complete questionnaires at our clinical research suite at UTHealth's Biomedical and Behavioral Sciences building (BBSB) at [name] or at UTHealth CRU at Memorial Hermann-TMC, Houston. University of Texas Health Science Center at Houston Memorial Hermann-TMC [name] or at UT Health Harris County Psychiatric Center (HCPC)

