Placement of IV: For both of the infusion days, after the initial evaluation is done, patients will be placed one intravenous line in each arm. One line will be used for the ketamine infusion and the other line will be used for the collection of blood samples and to reduce discomfort for patients with frequent blood draws. If the sample is not obtained from the IV line due to clotting, the patient will be asked if they would like to have a blood draw using a BD Vacutainer.

Medical Monitoring: During the infusion, patients will receive continuous monitoring from the nurse and the attending and after the completion of 40 min infusion, patients will rest for two hours under the observation of clinical nurse and reassessed again by anesthesiologist/psychiatrist (advance life support trained) at 2 hours after infusion. Patients will be discharged from the hospital unit between 2-4 hours after the infusion with a responsible adult for the study visit. Patients will be contacted on days 1, 2 and 7 post-infusion for a follow-up assessment of mental state by telephone and will be scheduled for study visits.

Stopping Rules: Any worsening of depression symptoms - if patients score a 3 on item 3 of the HDRS or 3 on item 10 of the MADRS or total HDRS score (first 21-items) increases by 5 points or more from one visit to the next weekly visit. The C-SSRS will be administered to monitor suicidal ideation and behavior. Increased observation consists of daily phone calls with study physicians and/or increasing visit frequency based on the PI's clinical judgment.

Blood tests: Ketamine and norketamine plasma levels will be collected before and 30 minutes, 2 hours and 4 to 5 hours after the infusion. Samples will be stored at BBSB for analysis. Analyses will be performed by Gas Chromatograph-Mass Spectrometer (30).

Clinical measures - Clinical rating and questionnaires will be administered. Treatment response will be operationally defined as 50% improvement from baseline in the HAM-D17 scores.

POTENTIAL RISKS/DISCOMFORTS

Diagnostic procedures and questionnaires: Some of the questions asked during the screening may be considered sensitive information, including drug use history and psychiatric history. Answering these questions may be psychologically discomforting to some subjects. There are also risks associated with loss of confidentiality.

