DATA ANALYSIS PLAN - General Data Analysis: The data analytic strategy will use generalized linear modeling. Statistical analyses will use SAS v.9.3. Preliminary data analyses will inspect baseline, treatment from baseline differences as well as correlations between baseline variables and specified outcomes. Baseline characteristics will be compared within groups using Student's t-tests for continuous data and chi-square tests for categorical data.

Sample size justification: our power calculation is guided by a previous study - intravenous ketamine in TRD patients (28) with effect size (Cohen's $d = 1.46$) or Brexanolone in PND (effect size 1.2) (12, 32). For an effect size 1.2, a total of 10 PND patients will be required for within-subject design with probability 95 % that the study will detect a treatment difference at a one-sided 0.05 significance level.

Hypothesis: Based on previous studies (33, 34) and our pilot Ketamine TRD patient data, we predict that ketamine infusion compared to baseline will significantly decrease HAM-D scores in PND patient at 24 hrs. The severe anxious subtype will have prominent improvement.

Analysis: We will use linear regression to assess associations between improvements in depressive symptoms (change in the HAM-D from baseline using LOCF). A paired t-test was performed to evaluate the key efficacy measure - change from baseline in HAMD total score. We will also perform a secondary analysis comparing change from baseline to endpoint using last observation carried forward (LOCF) using a paired sample t-test. Secondary outcomes are safety and tolerability measures, including treatment-emergent AEs and changes from EPDS, GAD-7, PHQ-9, and C-SSRS. We will also investigate specific markers for treatment response.

Alternate plans: The proposal applies the widely used ketamine sub-anesthetic dose (0.5 mg/kg) as a treatment for PND. If the effect is less clear or patient experiences any adverse effects, alternate strategies will be explored (two doses of ketamine instead of single or low dose 0.3 mg/kg if adverse effects etc. respectively). Patient safety and tolerability will be the most important guiding principle. This will require an amendment in the protocol and an updated consent.

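### The C-SSRS is scheduled only at screening and after each infusion, so single-dose change has no same-day pre-dose baseline and no routine rating follows either infusion day

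*Combined protocol and SAP*

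**What the plan says.** The Stopping Rules paragraph under Methods gives the C-SSRS its role: "The C-SSRS will be administered to monitor suicidal ideation and behavior". It sets no timing and no C-SSRS threshold. The numeric suicidality triggers there are a score of 3 on HDRS item 3 or on MADRS item 10.

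The Analysis paragraph of the Data Analysis Plan lists, among secondary safety and tolerability outcomes, "treatment-emergent AEs and changes from EPDS, GAD-7, PHQ-9, and C-SSRS". It names no time point or baseline for any of them.

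The schedule of assessments marks the C-SSRS at screening, after infusion 1 and after infusion 2. The sentence below the schedule says "All of the above clinical questionnaires will be completed at the screening visit as well as on the ketamine infusion day", with the SCID-I excepted. It does not say whether the infusion-day questionnaires come before or after dosing.

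On timing, Research Design and Methods says "There will be a minimum 7 days between the 2 infusions" and "Extension of the timeline can occur depending on the time between the screening visit and the first infusion dose". After the first infusion there is one call, a day later; "after the second infusion, patients will be contacted one day after and 7 days after the infusion". Those calls cover physical health, adverse events and mood questionnaires. The Medical Monitoring paragraph describes calls about mental state on days 1, 2 and 7. Neither account of the calls names the C-SSRS.

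**The concern.** A safety outcome defined as change needs a baseline close to the exposure and a rating far enough after it to register an effect. As scheduled, the C-SSRS has neither around a single dose. The only untreated value is the screening one, which is taken on a different day from the infusions and at an interval that the protocol leaves open. The post-dose value is taken on the dosing day, with discharge planned 2 to 4 hours after the infusion. The protocol's own risk section reports, for the 4 hours after an infusion, a sense of strangeness or unreality in 58.3% and sleepiness in 48.5%.

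The days that follow matter as well. The Background cites 71% responders at 24 hours, with effects persisting in up to 35% at 7 days. A patient whose improvement fades, or whose ideation returns, would do so when the scale named for the purpose is not routinely in use. The Background also describes severe perinatal depression as carrying raised risk of self-harm and suicide. The exclusion criterion removes only serious and imminent risk, so patients with lesser ideation can be enrolled.

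**Working it through.** The plan gives no figure on this point to reproduce. The check is a reading of the schedule and a count.

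**1. Columns.** The header has 8 assessment columns: 1 screening + 2 for infusion 1 (before, after) + 2 for infusion 2 (before, after) + 3 calls. The rows in the readable text have 7 cells, so one call column was lost when the table was extracted and two call cells per row can be read.

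**2. Marks in the 7 readable cells.**

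| Row | Screening | Before infusions | After infusions | Readable calls | Total |
|---|---|---|---|---|---|
| C-SSRS | 1 | 0 of 2 | 2 of 2 | 0 of 2 | 3 |
| HAM-D-17, MADRS, EPDS, GAD-7, BDI (each) | 1 | 2 of 2 | 2 of 2 | 2 of 2 | 7 |
| AE report | 1 | 0 of 2 | 2 of 2 | 2 of 2 | 5 |

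The AE row has blank pre-infusion cells and marked call cells. Cell positions therefore appear to have survived extraction, and the C-SSRS blanks are unlikely to come from it.

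**3. Planned ratings.** 3 per patient × 10 patients = 30. Of these, 10 are untreated (screening) and 2 × 10 = 20 are on a dosing day after an infusion. None is marked before dosing on an infusion day, and none at a readable call.

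**4. Age of the baseline.** Let S be the screening value and A and B the ratings after the two doses.
- Infusion 1: the only earlier value is S. Its age is limited only by the 3-month cap on total commitment. If that cap includes the last call, the limit is 3 months less 14 days (7 between infusions + 7 of follow-up).
- Infusion 2: S is at least 7 days older again, and the first dose lies in between. The only other earlier value is the rating after infusion 1, which is at least 7 days old and was taken on a dosing day under the other dose.

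**5. What cancels and what does not.**
- Between doses: (A − S) − (B − S) = A − B, so the age of S does not matter. The dose order is also randomized, "with the order being randomized and balanced across subjects".
- Single dose: A − S keeps everything that happened between screening and that infusion.

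**6. Recall windows if ratings are added at the pre-infusion and call contacts (since-last-contact form).**
- Before infusion 1: the variable screening-to-infusion interval.
- Before infusion 2: at least 7 − 1 = 6 days, counted from the day-1 call.
- Day-1 call: about 1 day, in both periods.
- Day-7 call after infusion 2: 7 − 1 = 6 days.

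A pre-infusion-to-day-1 score difference would set a window of 6 or more days (infusion 2), or of variable length (infusion 1), against one of about 1 day. The shorter window alone can lower the recorded ideation and look like benefit. The two day-1 ratings have matching windows.

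**The case against.** **The outcome can be computed as written.** The Analysis paragraph sets no time point for the C-SSRS and no hypothesis concerns it. The 24-hour target belongs to HAM-D and, under Hypothesis 2, to HAM-A and EPDS. Screening-to-post-infusion change can be calculated from the schedule as it stands. This is correct. A reader might infer that the listed outcome cannot be obtained or that a 24-hour commitment has been broken, and the documents support neither. What remains is a weak baseline and a late gap.

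**Safety does not rest on the C-SSRS alone.** HDRS item 3 and MADRS item 10 carry the numeric triggers, and both scales are marked before dosing and at the readable calls. There is also an eligibility review before each infusion, psychiatrist evaluation before and after it, adverse-event questioning by phone, mental-state calls on days 1, 2 and 7, and daily physician calls under increased observation. This stands in full and limits the consequence. It does not supply C-SSRS data.

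**The Stopping Rules sentence has another reading.** It sits between the triggers and the description of increased observation, so it may mean that the scale is also used for patients under escalation. That is possible. The counts above therefore describe the routine schedule only.

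**The infusion-day sentence could allow a pre-dose rating.** It does not require one, and the table places the C-SSRS after the infusion.

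**One call column cannot be read.** This is also correct. That its C-SSRS cell is blank is a likely inference from the neighboring cells, not an observation.

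**Conclusion.** The point holds as a cheap, worthwhile improvement to a secondary safety measure. In the routine schedule the C-SSRS has 3 marks, against 7 for the main mood scales. Single-dose change has to start from a screening value of variable age, and for infusion 2 it spans the first dose. No C-SSRS is routinely taken after either infusion day, as far as the cells can be read.

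Two stronger conclusions might be drawn, and neither is supported. One is that suicidality goes unmonitored after infusion 2. In fact a C-SSRS is scheduled that same day after dosing, and the item-level triggers, calls and adverse-event questions continue. The other is that the dose comparison is compromised. The screening value cancels from it, so the post-infusion contrast is unaffected by the missing baseline.

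The conclusion assumes that the schedule is followed as marked, that the unreadable call cell matches its neighbors, and that no C-SSRS is given outside the schedule except possibly under increased observation.

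**What to change.** In the schedule of assessments, mark the C-SSRS before infusion 1, before infusion 2, at the day-1 call after each infusion and at the day-7 call after infusion 2. Keep the existing post-infusion ratings. Use the since-last-contact form at the added contacts and state the recall window at each one.

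In the Analysis paragraph, define the outcome as treatment-emergent or worsened ideation or behavior relative to that period's pre-infusion rating. Compare doses on the day-1 ratings, whose windows match. Do not use a simple pre-infusion-to-day-1 score difference.

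The cost is a schedule amendment and 2 pre-infusion + 2 day-1 + 1 day-7 = 5 short ratings per patient, or 5 × 10 = 50 in total. All fall at contacts already planned, so no visits are added. The downside is extra time at those contacts, which the documents do not quantify. The change does not remove any carry-over of the first dose into the pre-infusion-2 rating. Reporting the two pre-infusion ratings separately would let a reader see it.

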Severe Perinatal Depression (PND) is a major depressive episode that occurs during pregnancy or onset within 12 months of the birth of a child. The prevalence of severe PND in the general population is estimated to be 5-10% (2). PND is a seriously disabling condition and can increase the risk of self-harm and health complications in mother can deleteriously affect the cognitive, emotional and social development of the child and increases the substantial economic burden on families and society (3). Selective Serotonin Reuptake Inhibitors (SSRIs) and psychotherapy are the main available treatment modalities for PND. While they are effective in some, it takes longer to work and half of the patients do not fully recover from depression. A faster onset of antidepressant action will be critical in enabling faster relief from depression and may increase the chance of full recovery. The main objective of this study is to investigate the rapid antidepressant effect of low sub-anesthetic dose of ketamine in PND.

Aims

To assess the safety, pharmacokinetics and antidepressant efficacy of a sub-anesthetic dose of intravenous ketamine in perinatal depression

A single, intravenous, sub-anesthetic dose of ketamine in patients with Treatment-Resistant Depression (TRD) induces a significant (50%) reduction in depression symptoms within 2 hours of administration with 65% of depressed patients respond by 24 hours and up to 35% maintain response until the end of 1 week (4). Our in-house pilot data, in consistent with worldwide studies, show that ketamine (N=5) can be safely administered to depressed patients and improves depression symptoms when assessed at 24 hrs post infusion. Ketamine has not been studied in the treatment of PND where there is a significant unmet need.

The dosing of ketamine (0.5 mg/kg over 40 mins) for antidepressant treatment was developed from research studies in the 1990s based on use in healthy participants (36). However, newer studies show some patients respond to lower dose and tolerated better (fewer side effects) by the patients (37). IV Ketamine reaches a peak within a few mins with an elimination half-life of 2–3 hrs (38). Ketamine's clearance may be 20% higher in women than in men (39). Ketamine is mostly metabolized in norketamine (80%) and persists more than 5 h after administration (38). It is important to evaluate ketamine's pharmacokinetic data in PND to improve safety for the

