breastfeeding mother and the baby. Ketamine and its metabolites will be evaluated in PND patients receiving ketamine 0.5 mg/kg or 0.2 mg/kg at 30 mins, 2 hours and 4-5 hrs after ketamine infusion. All adverse medical and psychiatric events with onset or worsening after the administration of ketamine will be included in the analysis.

The proposed experiment will be a proof-of-concept study in which we will evaluate the safety, pharmacokinetics, and efficacy of ketamine 0.5 mg/kg and 0.2 mg/kg over 40 minutes in a double-blinded and crossover fashion separated over one week (5) (dose used in antidepressant clinical trials) in PND patients who are not currently breastfeeding. The primary outcome measure of efficacy will be the Hamilton Depression Rating Scale (HAM-D-17) at 24 hours and additional secondary anxiety and mood scales. (6). Any adverse medical and psychiatric events will be recorded and summarized. Ketamine and its metabolites will be evaluated at 30 mins, 2 hours and 24 hrs.

Hypothesis 1): Ketamine will significantly decrease (>50%) in HAM-D17 scores at 24 hrs after infusion from baseline. The 0.5 mg/kg dose will be more efficacious than 0.2 mg/kg in improving depression symptoms.

Hypothesis 2) Ketamine will improve anxiety symptoms in PND (as measured using HAM-Anxiety and EPDS) at 24 hrs after infusion in patients with PND. Anxious subtypes are the most common subtype during a late postpartum period representing about 70 % of PND. (40)

Hypothesis 3) Ketamine infusion will be tolerated well by the patients with fewer side effects at 0.2 mg/kg compared to 0.5 mg/kg.

METHODS

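### No plasma sample is planned during or at the end of the 40-minute infusion, so the ketamine peak is not observed and a trapezoid AUC to 4.5 h would be about 8-9% low

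*Combined protocol and SAP*

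**What the plan says.** The Aims section opens with "To assess the safety, pharmacokinetics and antidepressant efficacy of a sub-anesthetic dose of intravenous ketamine in perinatal depression". It gives a half-life of 2-3 h and states that "IV Ketamine reaches a peak within a few mins". METHODS describes a "single intravenous infusion of Ketamine either at 0.5 mg/kg or 0.2 mg/kg over 40 minutes", each patient receiving both doses at least 7 days apart.

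The sampling times appear in four places:

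- Blood tests: "Ketamine and norketamine plasma levels will be collected before and 30 minutes, 2 hours and 4 to 5 hours after the infusion".
- Schedule of assessments, footnote 1: "Done at 30 minutes after infusion (+/-10), 2 hours after infusion (+/- 30 minutes) and 4.5 hours after infusion".
- Aims, first statement: "0.2 mg/kg at 30 mins, 2 hours and 4-5 hrs after ketamine infusion".
- Aims, second statement: "Ketamine and its metabolites will be evaluated at 30 mins, 2 hours and 24 hrs".

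All four put the first post-dose sample at 30 minutes, and none places a sample during or at the end of the infusion. They differ on the last sample: 4-5 h, 4.5 h or 24 h. Under Placement of IV each arm gets a line; one carries the drug and "the other line will be used for the collection of blood samples". Medical Monitoring has patients leaving the unit 2-4 h after the infusion.

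The Data Analysis Plan names no PK parameter (Cmax, AUC, clearance) and no PK method.

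**The concern.** A drug infused at a constant rate reaches its highest level when the infusion stops. With post-infusion times counted from that moment, about 70 minutes (60-80 with the window) separate the start of the infusion from the first post-dose sample. The whole rise, the peak and the first part of the fall lie in that gap. The largest ketamine value recorded is then a level already falling, and a trapezoid from the pre-dose sample to it cuts off the top of the curve.

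The trial compares two doses for safety and tolerability, and it would report a ketamine maximum below the true one without saying so. The protocol's section on infusion risks says that blood pressure and heart rate changes usually settle soon after the infusion, so no measured level stands close to them. An unsampled peak cannot be recovered once dosing is finished.

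**Working it through.** The plan gives no PK figure to reproduce, so the check asks what the planned samples would show.

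**Inputs from the protocol.** Infusion 40 min (METHODS); half-life 2-3 h (Aims); samples 30 min (±10), 2 h and 4.5 h after the infusion (Schedule of assessments, footnote 1). Counted from the start of the infusion, the times are 0, 70, 160 and 310 min.

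**Assumptions added here.** Constant infusion rate, one-compartment kinetics, "after the infusion" counted from its end, and the same times on both infusion days.

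**Step 1: observed maximum.** With k = ln 2 / half-life, k = 0.00578 per min (2 h) or 0.00385 per min (3 h). The level d minutes after the end, as a share of peak, is exp(-k·d).

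- d = 30: 0.841 (2 h) and 0.891 (3 h), so 11-16% below peak.
- Extremes of the window: d = 40 with 2 h gives 0.794; d = 20 with 3 h gives 0.926. So 7-21% below peak.

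**Step 2: AUC from the start of the infusion to 4.5 h after its end (peak = 1, units of peak × min).** True area = [40 - (1 - e^(-40k))/k] / (1 - e^(-40k)) + (1 - e^(-270k))/k.

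| | Half-life 2 h | Half-life 3 h |
|---|---|---|
| True area | 20.77 + 136.73 = 157.50 | 20.51 + 167.87 = 188.39 |
| Levels at 30 min, 2 h, 4.5 h | 0.841, 0.500, 0.210 | 0.891, 0.630, 0.354 |
| Linear trapezoid, planned samples | 29.43 + 60.34 + 53.27 = 143.04 | 31.18 + 68.44 + 73.76 = 173.38 |
| Error | -9.2% | -8.0% |
| With a sample at the end of infusion | 20.00 + 27.61 + 60.34 + 53.27 = 161.22 | 20.00 + 28.36 + 68.44 + 73.76 = 190.57 |
| Error | +2.4% | +1.2% |

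With log-linear interpolation on the falling part, the planned schedule is 9-12% low, and the schedule with the added sample is within 0.5%. The loss all comes from the first 70 minutes. Straight lines across the later decline overstate the area there and hide part of it.

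**Step 3: an early distribution phase (assumed; not in the documents).** Let a fast component with half-life 10-15 min carry a share p = 0.3-0.6 of the end-of-infusion level. The 30-minute level is p·exp(-k_fast·30) + (1 - p)·exp(-k·30). The lowest case is 0.6 × 0.125 + 0.4 × 0.841 = 0.41, and the highest is 0.3 × 0.25 + 0.7 × 0.891 = 0.70. The linear AUC to 4.5 h is then 13-29% low; one end-of-infusion sample brings it to +1% to +4%.

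**Step 4: last sample at 24 h.** The same linear trapezoid through 30 min, 2 h and 24 h gives 419.9 against a true 193.9 (2 h), or 518.0 against 279.2 (3 h): 86-117% too high. With log-linear decline it is 6-10% low. So the sign of the AUC error depends on which sampling statement is followed and on the interpolation rule.

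**Step 5: norketamine.** With assumed half-lives of 1-6 h, its modelled maximum falls 1.7 h or more after the end of the infusion, and the planned samples catch 95-100% of it.

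**Step 6: the other reading of time zero.** If times run from the start of the infusion, the 30-minute sample falls inside it, and the largest observed level is (1 - e^(-30k))/(1 - e^(-40k)) = 0.76-0.77 of peak. The peak is missed either way.

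**The case against.** The strongest reply is that the protocol promises no Cmax and no AUC, so the bias belongs to an analysis that the reader supplies. A one-compartment infusion model that uses the known 40-minute duration recovers the peak and the AUC in full if the kinetics are one-compartment. That stands as far as it goes: the AUC shortfall applies to a non-compartmental analysis and is not a property of the design. The model's protection is conditional, however. If the true curve has an assumed distribution phase (half-life 10-15 min, fast-to-slow coefficient ratio 1-4), the same model recovers only 79-95% of total AUC, and three post-dose samples give little means of telling which case applies. No PK model is planned.

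Four stronger readings are tempting, and the documents do not support them:

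- *All exposure results will be too low.* Norketamine is probably well covered, and with a 24 h last sample a linear trapezoid errs upward.
- *The dose comparison is distorted.* Under linear kinetics the proportional shortfall is the same at 0.5 and 0.2 mg/kg, so the exposure ratio survives. Hypothesis 3 compares side effects between doses, with no planned analysis against concentration, and the common side effects are described over the 4 hours after infusion, which the samples largely span.
- *The schedule contradicts the statement about a peak within minutes.* An infusion at constant rate peaks at its end in any case.
- *The data will make ketamine look safer than it is.* The Aims tie the PK data to safety for nursing mothers and their infants, just after noting that norketamine persists beyond 5 h. Late levels and the decline matter at least as much for that purpose.

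**Conclusion.** The point holds in a limited form. The ketamine peak is not observed under any of the sampling statements. On the protocol's half-life and one-compartment kinetics the recorded maximum is 11-16% low (7-21% across the window), and a linear-trapezoid AUC to 4.5 h is 8-9% low. The larger figures, 30-59% for the maximum and 13-29% for the AUC, rest on a distribution phase assumed here. Absolute ketamine levels are affected; norketamine, the dose ratio and the primary HAM-D-17 endpoint are not. It is a modest and inexpensive improvement to a 10-patient proof-of-concept study, worth making before dosing because no later analysis of the planned samples can observe the peak directly.

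Two conflicts bear on the same aim. The last sample is placed at 4-5 h, 4.5 h and 24 h in different sections, although the day-after contact is by telephone. The discharge time of 2-4 h also precedes a 4-5 h draw.

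**What to change.** 1. Add one draw at the end of the 40-minute infusion on both infusion days, through the sampling line in the other arm, and keep the other samples. Moving the 30-minute sample instead is not equivalent: the linear AUC is then 2-4% too high with one compartment and 8-28% too high with the assumed distribution phase.
2. State that post-infusion times count from the end of the infusion, and record actual clock times for the start and end of infusion and for every draw.
3. Name the PK parameters and method in the Data Analysis Plan: the observed end-of-infusion level as ketamine Cmax, and AUC to a stated last time by a stated rule (log-linear on the decline keeps the one-compartment error within 0.5%), or a specified infusion model.
4. Reconcile the last sampling time across Aims, Blood tests and the schedule footnote, and reconcile it with the discharge time under Medical Monitoring.

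Cost: 10 patients × 2 infusions = 20 extra tubes and assays, one line in the schedule and a short paragraph of analysis text. No extra needle, visit or staff is needed.
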